### **4.0 Patient Selection**

**Subject Inclusion Criteria:**

1. Histologically or cytologically confirmed diagnosis of adenocarcinoma of the prostate
2. Previous radiation therapy (any form) with curative intent for prostate cancer
3. Erectile dysfunction, as determined by an IIEF-5 score of <22
4. Normal testosterone (including men on testosterone replacement), defined as testosterone >150 ng/dl at the time of screening
5. Age  $\geq$ 18 years

6. Karnofsky Performance Status (KPS)  $\geq 70$ , or ECOG 0-2
7. Patients may be taking an HMG-coA-reductase inhibitor
8. Serum alanine aminotransferase (ALT) and aspartate aminotransferase (AST)  $\leq 3X$  upper limits of normal (ULN)
9. Creatinine Kinase  $< 5$  times ULN.
10. Normal renal function as defined below:

Normal renal function is defined as creatinine clearance  $\geq 30$  ml/min via the Cockcroft Gault Formula:

$$\text{Female CrCl} = \frac{(140 - \text{age in years}) \times \text{weight in kg} \times 0.85}{72 \times \text{serum creatinine in mg/dL}}$$

$$\text{Male CrCl} = \frac{(140 - \text{age in years}) \times \text{weight in kg} \times 1.00}{72 \times \text{serum creatinine in mg/dL}}$$

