**11.0 Biostatistics**

**A. Goal:**

The purpose of this trial and design is to provide inexpensive treatment for ED following XRT. While we hypothesize a smaller success rate than prescription ED treatments, this combination may be a less expensive alternative for those patients who do benefit. Three planned subgroups

will be enrolled, patients who are not on any statins at the time of enrollment, those on atorvastatin, and those on other statins. Patients will remain on study from enrollment until 1 year, disease relapse requires therapy, the physician withdraws the patient for safety reasons, or the patient withdraws for any reason.

Revision 2021. Since this trial was closed to accrual during the pandemic and new telemedicine practices and pandemic limitations are stifling accrual, this trial is being revised to enroll 50 patients with planned subgroups based on prior statin experience rather than the original 270 with 90 patients per statin cohort. This will still allow us to honor the patients already enrolled, learn something new, and also complete the trial in a reasonable amount of time under the new conditions. At the time of revision, there are 11 patients enrolled, and the first interim analyses as described in this revision allow the trial to continue.

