## **B. Endpoints**

### **i. IIEF-5 (International Index of Erectile Function)**

This validated instrument will be completed as per study calendar. The instrument categorizes ED severity into 5 categories as none (22-25), mild (17-21), mild to moderate (12-16), moderate (8-11), or severe (5-7). A patient will demonstrate improvement at any time point if his score goes up enough to move at least 1 category less severe compared to baseline. A patient with improvement will be considered to have a response. Patients who drop out of the trial without any measurements will count as a non-responder.

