**D. Interim Analyses for Safety and Futility**

Interim analyses will begin after 10 patients have been enrolled. Monitoring will then be performed every 10 patients to ensure that patients are exhibiting reasonable toxicity and efficacy rates to continue with the trial. Patients who receive treatment less than 8 weeks will still be counted in toxicity and futility monitoring as long as they received at least 1 dose of the study drug. For patients already on statins, this means the patient must have started the combination. For patients who are starting on atorvastatin, patients will count as long as they received at least one dose of atorvastatin. If the trial can continue after 40 patients, then interim analyses will be complete. Adverse events will continue to be recorded and reported for all patients. If the toxicity or efficacy rates are noted to be different among the patient subgroups, the same stopping rules may be applied to any subgroup of concern to discontinue enrollment of that subgroup.

A Bayesian sequential monitoring design (Thall et al. 1995 and 1998) will be used to monitor the trial for toxicity and futility. Calculations were performed in MultcLean 2.1.

Toxicities will be monitored assuming a prior probability of toxicity following Beta(1,1) against a constant rate of 30% as the maximum acceptable toxicity rate. Trial limiting toxicities (TOX) are any grade 3 or higher toxicities at least possibly related to the study drug that occur in the first 8 weeks of therapy. The trial will be terminated if  $\text{Prob}(\text{TOX} > 0.30 \mid \text{data}) > 0.95$ . Following this rule, the trial will be terminated according to the table below once the first 10 patients have enrolled.

Similarly, efficacy will be monitored assuming a prior probability of response following Beta(0.33,0.67) against a constant rate of 33% as the minimum acceptable response rate. A patient will have a response if there is documented improvement at any time point on the trial. The trial will be terminated if  $\text{Prob}(\text{Response} < 0.33 \mid \text{data}) > 0.975$ . Following this rule, the trial will be terminated according to the following table once the first 10 patients have enrolled.

If there are this many patients treated who are evaluable (i.e., have TOX or completed the first 8 weeks without TOX for TOX, or have at least one IIEF result post-baseline for response)	10	20	30	40

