Stop the trial if there are this many (or more) patients who have TOX	6	10	14	17
Stop the trial if there are this many (or fewer) patients who have responded.	0	2	5	7

The first 10 patients will be accrued before the first analysis. If 6 or more of the 10 patients have TOX events, stop the trial and the treatment will be declared as too toxic for this population. If there are 5 or fewer patients with TOX events and at least 1 patient with response, enroll the

next 10 patients and compare the number of patients with TOX and response against the table's rules.

The futility rule will be checked at the same time as the safety check even though the assessment time is later. As long it is safe and there are enough responses to continue, the trial will continue without delay. If there are not enough responses to continue but enough patients are pending response that it will be possible to continue once they are assessed, enrollment will hold until enough responses occur or enough patients go off study without response to prevent the possibility of passing the rule. Since response can occur at any of the planned times, a patient who was previously a non-responder can become a responder at a later follow-up and will count as a responder in the current analysis even if counted as non-responder in a previous analysis. A patient will not change from a responder to non-responder later.

The operating characteristics for these rules are summarized in the following table, based on simulations performed in Multc Lean Desktop version 2.1.

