**E. Analysis Plan**

Patients' baseline ED levels will be reported along with the proportion for patients who improve by at least 1 level according to the IIEF-5 for each time point measured. The proportion will be reported along with a 95% credible interval implementing a non-informative prior of beta(0.33, 0.67). Additionally, the proportion of patients who ever improve by at least 1 level will be reported overall. For secondary measures, the safety profile of the PAVE combination will be reported overall and for each planned subgroup based on prior statin treatment, with adverse events summarized by grade and time to onset to first grade 3 adverse event. Finally, the number of patients who drop out of the study to start an ED prescription medication will be reported. Exploratory analyses will be utilized to determine whether baseline patient features can predict response to PAVE or adverse events.

The Investigator is responsible for completing an efficacy/safety summary report, and submitting it to the IND Office Medical Affairs and Safety Group, for review and approval. This should be submitted every 10 evaluable patients, complete 8 weeks of study treatment until enrollment is complete

A copy of the summary should be placed in the Investigator's Regulatory Binder under "sponsor correspondence".

Important medical events as defined above, may also be considered serious adverse events. Any important medical event can and should be reported as an SAE if deemed appropriate by the Principal Investigator or the IND Sponsor, IND Office.

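### The stopping-table header leaves dosed men with no post-baseline IIEF-5 out of the futility count, while the endpoint definition scores them as non-responders; following the header tilts futility monitoring toward continuing

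*Combined protocol and SAP*

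**What the plan says.** Four places in the combined protocol and SAP bear on who counts for futility.

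- **Stopping-table header, Section 11.0 D.** For response, the evaluable men are those who "have at least one IIEF result post-baseline for response".
- **Endpoint definition, Section 11.0 B.i.** "Patients who drop out of the trial without any measurements will count as a non-responder".
- **Text of Section 11.0 D.** "Patients who receive treatment less than 8 weeks will still be counted in toxicity and futility monitoring", provided they took at least one dose. It does not say how they are scored for response.
- **Hold rule, Section 11.0 D.** If responses are too few but some are pending, enrollment waits for more responses or until "enough patients go off study without response to prevent the possibility of passing the rule".

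Table 1 (Section 8.0) schedules the IIEF-5 at baseline and then first at 3 months (± 2 weeks), with none at 6 weeks. Section 11.0 A reports 11 men enrolled at the 2021 revision and that "the first interim analyses as described in this revision allow the trial to continue". The looks at 20, 30 and 40 are therefore the ones still affected.

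**The concern.** Entry requires "Erectile dysfunction, as determined by an IIEF-5 score of <22" (Section 4.0), so every enrolled man has a baseline score. A man without any measurements in the sense of 11.0 B.i can then only be one with no post-baseline score. That is exactly the man the header leaves out.

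Such men are foreseeable. Section 8.0 takes men with certain grade 3 or higher toxicities off the study, this can happen before the 3-month questionnaire, and Table 1 schedules no IIEF-5 at removal. Men who stop drug but still return a questionnaire are not affected. Men still on study and awaiting their first one are simply pending.

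Leaving out men whom the endpoint scores as failures can only raise the observed response proportion. An inactive regimen is then less likely to be stopped, and two people applying the text to the same data could reach different denominators.

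**Working it through.** **Inputs.** From Section 11.0 D: prior Beta(0.33, 0.67), reference rate 0.33, cutoff 0.975, boundaries 0/2/5/7 at 10/20/30/40. From 11.0 C: maximum 50 men. Assumed, because the documents give no figure: a share d = 5%, 10% or 20% of dosed men have no post-baseline IIEF-5, and all of them are failures under 11.0 B.i.

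**Step 1: the plan's own figures.** The rule stops if P(p < 0.33 | Beta(0.33 + x, 0.67 + n − x)) > 0.975. The largest x meeting this is 0, 2, 5 and 7 at n = 10, 20, 30 and 40, as printed. An exact binomial recursion over the four looks, with toxicity and response independent, gives at toxicity 0.10 early-stop probabilities of 0.814, 0.277, 0.063 and 0.004 for response 0.15, 0.25, 0.33 and 0.45. The plan prints 0.81, 0.28, 0.06 and 0.004. All 25 printed stop probabilities reproduce to within 0.005.

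**Step 2: header followed, looks waiting for 10/20/30/40 evaluable men.** With an all-dosed response rate r, the rate among assessed men is r/(1 − d). For r = 0.15 this is 0.15/0.95 = 0.158, 0.15/0.90 = 0.167 and 0.15/0.80 = 0.1875. For r = 0.25 it is 0.263, 0.278 and 0.3125. The same recursion is run at these rates.

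**Step 3: header followed, looks every 10 dosed men, unmeasured leavers dropped.** Here the number assessed is random. The exact joint path of (assessed, responders) is followed in blocks of 10 dosed men, and the posterior rule is applied to whatever number is assessed.

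Futility stop probability:

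| True all-dosed response | Reading | d = 0 | 5% | 10% | 20% |
|---|---|---|---|---|---|
| 15% | Looks wait for evaluable men | 0.81 | 0.78 | 0.73 | 0.61 |
| 15% | Looks every 10 dosed men | 0.81 | 0.76 | 0.70 | 0.56 |
| 25% | Looks wait for evaluable men | 0.28 | 0.22 | 0.17 | 0.09 |
| 25% | Looks every 10 dosed men | 0.28 | 0.22 | 0.18 | 0.12 |

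**Step 4: given that the first look is passed** (step 2 reading). The formula is (total stop − stop at look 1)/(1 − stop at look 1). At 15% and d = 0, look 1 stops with probability 0.85^10 = 0.197, so (0.814 − 0.197)/(1 − 0.197) = 0.77. With 5/10/20% unassessed this becomes 0.73/0.68/0.55. At 25% it goes from 0.23 to 0.19/0.14/0.07.

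**Step 5: single looks.** 5/30 gives 0.9805 (stop) and 5/29 gives 0.9747 (continue). 2/20 gives 0.9934, and four men must be left out before the decision changes (2/16: 0.9749). 7/40 gives 0.9875, and 7/38 still stops at 0.980. At the first look, 0/10 and 0/8 both stop.

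**The case against.** The strongest reply is that the plan already leans to the right answer. The endpoint definition, the text of 11.0 D and, by implication, the hold rule all count these men, and one parenthesis in a table header is the outlier. That is fair, and it is why the repair is small. But no passage says which wording governs, and the header is what defines the denominator against which 0/2/5/7 are read.

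The size is also open to challenge. It rests on an assumed unassessed rate, and Table 1 lets the questionnaire be completed at home and sent by email or fax, so leaving treatment need not mean no score. The second reading in the table applies the posterior at counts that the stopping table does not list. Both points stand. The direction does not depend on them.

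A reader might infer three stronger things that the documents do not support:

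- **That the operating characteristics are wrong.** They reproduce. The table does not say whether its response rates describe all dosed men or only assessed men. If the latter, the header agrees with it, and the bias is relative to the 11.0 B.i endpoint only.
- **That looks would be pushed late and the last might never be reached.** This needs looks to wait for IIEF-evaluable men. Section 11.0 D ties looks to every 10 patients and checks futility together with safety.
- **That the primary estimate is biased.** The primary objective is estimation, and 11.0 B.i already scores these men as non-responders there.

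**Conclusion.** The inconsistency is in the current text and should be corrected before the next look. Following the header makes futility monitoring more lenient than the endpoint it is meant to monitor. The loss in stop probability at 15% true response is 0.03 to 0.05 if 5% of dosed men are unassessed (0.81 to 0.78 or 0.76) and 0.20 to 0.25 if 20% are (0.81 to 0.61 or 0.56). It is nil if there are no unmeasured leavers, and a single look rarely changes. Confidence is high on the conflict and its direction. The size is conditional on the assumed rates.

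A secondary conflict of the same kind affects toxicity. The text of 11.0 D counts men after one dose, while the header requires that they "have TOX or completed the first 8 weeks without TOX for TOX". The two differ for men lost before week 8 without a recorded TOX. A reader might infer that the documents point to one particular toxicity denominator, such as observation to week 8 on or off drug. They do not. The reporting rule in 11.0 E reads "This should be submitted every 10 evaluable patients, complete 8 weeks of study treatment until enrollment is complete", which refers to weeks on treatment. The 6-week check (± 2 weeks) need not reach week 8. Table 1 times follow-up from the start of all three drugs together, not from first dose.

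**What to change.** **Response.** Change the header so that every man with at least one dose is evaluable for response once he has a post-baseline IIEF-5 or has left the study, and counts as a non-responder if he left without one. Men still on study and awaiting their first post-baseline IIEF-5 stay pending. Keep 0/2/5/7, and add one sentence saying that the response rates in the operating-characteristics table count such dropouts as failures. With that definition the printed figures hold. No new boundaries or patients are needed.

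**Cost.** If 33% was meant as the rate among assessed men only, the all-dosed rate is 0.33 × (1 − d), or 31.4/29.7/26.4% at 5/10/20% unassessed. The futility stop probability then rises from 0.063 to 0.088/0.122/0.221 (given the first look is passed, from 0.045 to 0.067/0.095/0.182). The team should accept this knowingly.

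**Toxicity.** Reconcile the text and the header of 11.0 D before the next look so that both state one denominator, and check the reporting rule in 11.0 E against it. Which denominator to use is for the trial team to decide.

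### The futility table's definition of an evaluable patient contradicts the hold clause beneath it and the rule for men with no IIEF-5, so the same data can give different stopping decisions

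*Combined protocol and SAP*

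**What the plan says.** Section 11.D tests response "against a constant rate of 33% as the minimum acceptable response rate". After the first 10 patients, "Monitoring will then be performed every 10 patients", ending at 40. The table stops the trial for futility at 0, 2, 5 or 7 responders (or fewer) among 10, 20, 30 or 40 evaluable patients.

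Four statements decide who is in those counts:

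- **Table header (11.D).** A treated man is evaluable for response if he "have at least one IIEF result post-baseline for response". Table 1 schedules the IIEF-5 at 3, 6, 9 and 12 months after baseline, so this is normally met at 3 months.
- **Hold clause (11.D, under the table).** If responses are too few but enough are still awaited, "enrollment will hold until enough responses occur or enough patients go off study without response to prevent the possibility of passing the rule". The next sentence adds that "a patient who was previously a non-responder can become a responder at a later follow-up"; the reverse change is not allowed.
- **Early leavers (11.D).** Men treated for less than 8 weeks stay in toxicity and futility monitoring if they took at least one dose.
- **No measurements (11.B.i).** "Patients who drop out of the trial without any measurements will count as a non-responder".

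Under 11.A, men stay on study for one year unless relapse needing therapy, a safety withdrawal or their own withdrawal comes first.

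**The concern.** The header and the hold clause answer one question differently: is a man with a 3-month score, no improvement and nine months of follow-up left settled or pending? By the header he is already evaluable and counts against the treatment. By the closing words of the hold clause he is unsettled until he responds or leaves the study. The opening of that clause does not help, because it speaks of patients who will let the rule be passed once assessed, and a man with a 3-month score has in one sense been assessed. Nothing states outright that a non-responder still on study is pending.

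The second mismatch does not depend on how the hold clause is read. A man who takes a dose and leaves before his first IIEF-5 is in futility monitoring under 11.B.i and the early-leaver sentence, but outside it under the header.

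This rule can end the trial. Two teams acting in good faith could decide differently, and only one of the two readings matches the published operating characteristics.

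**Working it through.** **1. The plan's boundaries.** With prior Beta(0.33, 0.67) and x responders among n, the posterior is Beta(0.33 + x, 0.67 + n − x). The trial stops if P(response < 0.33) exceeds 0.975.

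| n | Largest x that stops | P | Next x | P |
|---|---|---|---|---|
| 10 | 0 | 0.998 | 1 | 0.963 |
| 20 | 2 | 0.993 | 3 | 0.971 |
| 30 | 5 | 0.981 | 6 | 0.948 |
| 40 | 7 | 0.988 | 8 | 0.969 |

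The tabulated 0, 2, 5, 7 are confirmed.

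**2. The plan's stop probability.** An exact binomial recursion over the four looks at a true response of 0.33 gives futility stops of 0.0182 + 0.0133 + 0.0249 + 0.0064 = 0.0628. The toxicity rule at a true rate of 0.10 adds 0.0002, so 1 − (1 − 0.0628)(1 − 0.0002) = 0.063, against the stated 0.06. All 25 stated probabilities reproduce within rounding and simulation error. This calculation gives every man his final response status at each look.

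**3. Two readings of the same data.**

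- Twenty men have 3-month scores, 2 have responded and 18 remain on study. Header and table: 2 of 20 is on the boundary, so stop. Hold clause: the 18 may still respond, so hold.
- Twenty men are treated, 3 leave before any IIEF-5, and 2 of the other 17 respond. Header: 17 evaluable, so the 20-patient column is not reached. Sections 11.B.i and 11.D: 2 of 20.

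**4. Size of the first conflict.** Two inputs are not in the documents and are assumed: the share of eventual responders who respond by 3 months (100%, 75% or 50%, the rest spread equally over 6, 9 and 12 months) and accrual (1, 2 or 4 patients per month, no dropout). Staggered entry was simulated at a true response of 0.33, futility rule only, 6,000 trials per cell (standard error about 0.003 at 6% and 0.006 at 41%). Later responses count under both readings.

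| Share by 3 months | Header governs: 1 / 2 / 4 per month | Hold until off study at 12 months |
|---|---|---|
| 100% | 0.06 / 0.06 / 0.07 | 0.06 / 0.06 / 0.07 |
| 75% | 0.11 / 0.14 / 0.19 | 0.06 / 0.06 / 0.07 |
| 50% | 0.18 / 0.29 / 0.41 | 0.06 / 0.06 / 0.07 |

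Unrounded, the last column runs from 0.057 to 0.068. The header column assumes that enrolment pauses at each look until first scores are in. If accrual continues and each look is taken when the last of its 10, 20, 30 or 40 men reaches 3 months, the results at 4 per month become about 0.2 (75%) and 0.52 (50%).

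**5. The first look.** Section 11.A reports 11 enrolled at the 2021 revision and the first interim analysis passed. Given that, the remaining futility-stop chance with final responses is (0.0628 − 0.0182) / (1 − 0.0182) = 0.045. The figures in step 4 include all four looks and so overstate what remained.

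**The case against.** The strongest reply is that the plan already deals with delayed response. The hold clause was written for it, ends a hold only on response or on leaving the study, and is followed by a sentence explaining that non-responders can convert. Text that specific should outrank a parenthesis in a table header. On that reading a 3-month non-responder still on study can cause a hold but not a stop, and no operating characteristic changes. Likewise, the one-dose sentence and 11.B.i together already place unmeasured leavers among the non-responders.

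Most of this stands. It shows which reading was probably meant and why the stated 0.06 can be kept. It does not remove the contradiction: the header defines the denominators of the table that triggers the stop, and it says something different on both points.

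A reader might go further and infer that the stated 6% is wrong, or that 3-month non-responders will stop the trial far more often. The documents do not support that, because the excess arises only if the header overrides the hold clause. Nor do they support the extreme case in which only 3-month status is ever used. That would give 0.29 at a 75% share and 0.74 at 50%, but the plan expressly counts later responses.

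**Conclusion.** Wrong as written: the stopping rule contradicts itself on who counts for futility. Under the hold clause read as a whole, the futility stop at a true response of 33% is about 6% and the published table is sound. The 0.06 is the row for true toxicity 0.10; the table gives 0.07 at 0.20 and 0.17 at 0.30, where toxicity stops add to it.

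If the header is applied instead, the futility stop is about 11% to 20% with 75% of responders seen by 3 months and about 18% to 52% with 50%. There is no excess if all respond by then. These ranges rest on assumed response timing and on accrual of 1 to 4 patients per month, and they include a first look that was already passed. They show what the wording puts at risk, not how the trial is expected to behave. The conflict over men with no IIEF-5 is certain from the text; its size depends on dropout, which the documents do not give.

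**What to change.** Replace the response part of the table header in 11.D. A treated man counts for futility when he has responded, or when he has gone off study without response, which includes completing the 12-month IIEF-5. Add that every other treated man is pending under the hold clause, whether or not he has an interim score, and that a treated man who leaves with no post-baseline IIEF-5 counts as a non-responder, as 11.B.i says.

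Boundaries, sample size and operating characteristics are unchanged. The cost is time. In the simulation holds are about equally common under either reading: with a 75% share, at least one hold in 31%, 67% and 99% of trials under the header and 32%, 66% and 99% under the hold clause, at 1, 2 and 4 patients per month. Each hold may last longer, since a non-responder stays pending for up to 12 months rather than 3. The hold clause already accepts that delay.

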**Table 1: Patient assessment schedule**

Test	Baseline *** (within 8 wks of enrollment)	6 wk* ± 2 wks	3 mo* ± 2 wks	6 mo* ± 2 wks	9 mo* ± 2 wks	12 mo* ± 2 wks	18 mo ± 4 wks*
H&P	X			X		X	X
BP, Pulse, Respiratory Rate	X	X	X	X	X	X	
KPS or ECOG	X			X		X	
IIEF-5****	X		X	X	X	X	
CTCAE V4.03**	X	X	X	X	X	X	
Hepatic panel	X	X	X	X	X	X	
CK 	X	X	X	X	X	X	
BUN, Creatinine, calculated GFR, CBC, PT, PTT, INR, Testosterone	X	X	X	X	X	X	

In addition to scheduled testing, obtain at any time patient notes muscular symptoms

\*follow up times start from the day patient begins taking all 3 drugs concurrently. Can be done over the phone or in person, in the event that follow up can only be done over the phone, physical exam, KPS or ECOG, and vitals do not have to be obtained. Labs could be drawn at outside facility and IIEF-5 questionnarire can be completed at home and both can be submitted via secure email or fax.

\*\*selected items with CTCAE grade 2 or higher: blurry vision, abdominal distension, abdominal pain, bloating, diarrhea, dyspepsia, flatulence, gastrointestinal pain, nausea, vomiting, malaise, pharyngitis, urinary tract infection, bruising, bleeding, arthralgias, bone pain, generalized muscle weakness, myalgia, headache, rash (maculopapular), flushing, chest pain, palpitations, dyspnea, cough, wheezing, lower extremity edema. This assessment can be done either over the phone or in person.

\*\*\*please refer to section 5.0 for pre-treatment evaluation

\*\*\*\*please refer to the appendix for the IIEF-5 questionnaire

D. **Modification of statin dosing**

1. discontinue if transamimases become  $\geq$  3 times ULN
2. discontinue if creatine kinase becomes  $\geq$  5 times ULN
3. If not on a statin prior to enrollment in the trial, discontinue if signs or suspicion of cardiovascular issues appear per the discretion of the treating physician.

For other side effects listed in section 8 above:

- a. if dose is  $\geq$ 20mg and if toxicity is Grade 2, decrease dosage by 50%. If toxicity resolves or decrease to Grade 1, maintain atorvastatin at this lower dose. If toxicities are  $\geq$ Grade 3, stop atorvastatin and the patient should be removed from the study.
- b. If dose=10mg, hold atorvastatin. If toxicity resolves or decrease to Grade 1, restart at 10 mg every other day. If toxicities are  $\geq$ Grade 3, stop atorvastatin and the patient should be removed from the study.

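### Cheap improvement: suspend enrolment as soon as the TOX count among the next look's patients reaches that look's stopping number, instead of filling the block of 10 first

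*Combined protocol and SAP*

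**What the plan says.** Section 11.D defines TOX as a grade 3 or higher event, at least possibly related to study drug, in the first 8 weeks. The criterion is a posterior probability above 0.95 that the TOX rate exceeds 0.30, under a Beta(1,1) prior. The next sentence ties that criterion to fixed numbers: "Following this rule, the trial will be terminated according to the table below once the first 10 patients have enrolled". The schedule is in blocks: "Monitoring will then be performed every 10 patients to ensure that patients are exhibiting reasonable toxicity and efficacy rates to continue with the trial". The numbers that stop the trial are 6, 10, 14 and 17 at 10, 20, 30 and 40 patients. After a passed look, the team enrols the "next 10 patients and compare the number of patients with TOX and response against the table's rules".

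The table header counts patients as evaluable for toxicity if they "have TOX or completed the first 8 weeks without TOX for TOX". A man with TOX therefore counts straight away, while a man without it counts only after 8 weeks.

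The one enrolment hold in section 11.D concerns pending responses: "enrollment will hold until enough responses occur or enough patients go off study without response to prevent the possibility of passing the rule". The investigator's summary to the IND Office (section 11.E) follows the same blocks: "This should be submitted every 10 evaluable patients, complete 8 weeks of study treatment until enrollment is complete". Section 11.A records that 11 patients had been enrolled at the 2021 revision and that the first look had been passed.

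**The concern.** A TOX event does not reverse unless its grade or attribution is revised. Once the count among the patients of the next look equals that look's stopping number, the result of the look is settled, and patients enrolled after that point cannot change it. Section 11.D gives no instruction for this situation. The other safeguards act elsewhere: section 8.0 removes the individual patient at grade 3 or higher, and section 10.0 governs reporting of serious events. Neither suspends accrual on the TOX count.

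At stake is a small number of men who would start a three-drug regimen for a condition that is not life-threatening, after the trial's own rule has already decided that it must stop for toxicity.

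**Working it through.** **1. Reproduce the plan's boundaries.** For toxicity, take the smallest k with P(p > 0.30 | Beta(1+k, 1+n−k)) > 0.95. At n = 20, k = 10 gives 0.974 and k = 9 gives 0.932, so the number is 10. The same step gives 6, 14 and 17 at n = 10, 30 and 40. For futility, the largest k with P(p < 0.33 | Beta(0.33+k, 0.67+n−k)) > 0.975 is 0, 2, 5 and 7. All eight match the plan.

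**2. Reproduce the operating characteristics.** A binomial recursion with looks only at 10, 20, 30 and 40, and TOX independent of response, gives Pr(stop early) of 0.0711, 0.1718, 0.5386 and 0.8985 at response 0.33 and TOX 0.20, 0.30, 0.40 and 0.50. The plan states 0.07, 0.17, 0.54 and 0.90. The published table therefore assumes block looks, with no stopping in between.

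**3. Is the plan's criterion already met when a number is reached early?** Yes. P(TOX > 0.30) is 0.994 at 10/17, 0.983 at 10/19, 0.983 at 14/29 and 0.968 at 17/39.

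**4. Most men that can be spared.** Passing a look caps the count carried forward.
- 20-patient look: at most 5 TOX in the first 10, so 10 is reached at man 15 at the earliest, sparing 20 − 15 = 5.
- 30-patient look: at most 9 in the first 20, so 14 is reached at man 25 at the earliest, sparing 5.
- 40-patient look: at most 13 in the first 30, so 17 is reached at man 34 at the earliest, sparing 6.

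**5. Average gain if TOX is known at once.** Simulated trials that pass the first look, response 0.33:

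| True TOX | Pr(toxicity stop) | Men spared per stop | Mean N, plan → fix | Men spared per trial |
|---|---|---|---|---|
| 0.30 | 0.071 | 1.206 | 47.595 → 47.509 | 0.086 |
| 0.40 | 0.401 | 1.494 | 41.126 → 40.527 | 0.599 |
| 0.50 | 0.814 | 1.799 | 31.164 → 29.700 | 1.464 |

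The last column is the product of the second and third, and equals the difference in mean N. At TOX 0.20 the gain per trial is under 0.003.

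**6. Average gain with delayed knowledge.** The documents give neither the accrual rate nor the timing of TOX, so both are assumed. The first scheduled CTCAE check after baseline is at 6 weeks ± 2 (section 8.0, Table 1), and "follow up times start from the day patient begins taking all 3 drugs concurrently". Accrual is Poisson at 1, 1.5 or 2 men a month and pauses at each look until its patients are evaluable. The cells show mean men spared per toxicity stop when TOX becomes known uniformly over 8 weeks / at week 6 / at week 8:

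| Men per month | TOX 0.50 | TOX 0.40 |
|---|---|---|
| 1 | 1.2 / 1.0 / 0.8 | 0.95 / 0.8 / 0.6 |
| 1.5 | 1.0 / 0.7 / 0.5 | 0.8 / 0.5 / 0.4 |
| 2 | 0.8 / 0.5 / 0.3 | 0.6 / 0.4 / 0.2 |

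Across these cells, 45 to 84% of toxicity stops at TOX 0.50, and 53 to 87% at TOX 0.40, spare nobody.

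**7. If accrual does not pause.** Section 11.D requires no pause for toxicity: "As long it is safe and there are enough responses to continue, the trial will continue without delay". If enrolment runs on until the look's patients are evaluable, the delayed figures rise to 1.8–2.8 (TOX 0.50) and 1.5–2.6 (TOX 0.40) per stop, and to at most 0.17 per trial at TOX 0.30. These include men enrolled beyond the look's number.

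**8. Whose TOX counts.** With no pause, 2 men a month and onset uniform over 8 weeks, counting TOX in every enrolled man would raise Pr(stop early), given the first look is passed, from 0.114 to 0.160 at TOX 0.30. Limiting the count to the look's own patients leaves it at 0.114.

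**The case against.** The strongest reply is that this is a preference. The spacing is stated, the operating characteristics match it, and any rule with grouped looks admits some patients between them. The gain is also close to nil unless the regimen is far more toxic than section 2.0 suggests, since it describes the agents as generally well tolerated. Both points stand, and they are why this is offered only as an improvement. Even so, the plan tabulates true TOX rates of 0.40 and 0.50 and has a stopping rule for them; the change matters only where that rule is needed.

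The no-pause figures can be challenged too. Enrolling the next 10 is conditional on the look's result, and the remark about continuing without delay sits in a paragraph on pending responses. A pause is a fair reading, so the pause figures are the ones to rely on.

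A third objection is that the table counts evaluable patients, while a running count would follow enrolment order. The two sets can differ, but the conclusion does not. A man with TOX is evaluable at once, so 10 TOX events known among the first 20 enrolled before the look must all appear in the look at 20 evaluable patients. No extra stop is created.

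Finally, the summary to the IND Office is due only every 10 evaluable patients, so a stop between reports needs someone named to confirm the events. That is fair, and the proposed text names the investigator.

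**Conclusion.** The point holds as a low-priority improvement. As written, men can be enrolled after a toxicity stop at the 20-, 30- or 40-patient look has become certain. With a pause at each look, the expected number spared per trial is at most 0.09 at TOX 0.30 and negligible at 0.20. It becomes noticeable only at TOX 0.40 to 0.50, where 0.2 to 1.2 men are spared per toxicity stop with delayed knowledge and 1.5 to 1.8 with immediate knowledge. These figures assume response 0.33, TOX independent of response, a passed first look, and accrual and timing values that the documents do not supply. That the stop is certain, and that stopping probabilities do not change, depends on none of the accrual or timing values; it requires only that events are not re-graded or re-attributed.

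**What to change.** Keep the looks and boundaries, and add to section 11.D:

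> The investigator keeps a running count of TOX among the patients who make up the next look (the first 20, 30 or 40 enrolled). If that count reaches the look's stopping number (10, 14 or 17) before the look, enrolment is suspended at once and the investigator confirms grade and attribution; if they are confirmed, the trial stops for toxicity. TOX in patients enrolled beyond the look's number does not count toward it.

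The last sentence is needed to keep the tabulated Pr(stop early) valid. The tabulated sample-size percentiles become upper bounds in the model they were computed under, so no new simulation is required.

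The cost is three sentences and a tally of events that the investigator must already verify and attribute at grade 2 or higher (section 10.0). No committee or new IND Office task is needed. The one drawback is that a trial stopped for toxicity ends with slightly fewer men and slightly less precise estimates.
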